3.2 Statistical Analysis Issues

3.2.1 Time scales

The analysis will utilize two different time scales. “Calendar time” will be defined as time since enrollment of the first study participant. “Study time” will be defined as time from either the first

nasal swab (if the first swab result was negative) or 90 days after the first swab (if first swab positive). Note that while randomization would be the ideal origin for study time, some participants did not begin swabbing until days or even weeks into the study, and infection status and timing of infection cannot be determined prior to the initiation of swabbing.

3.2.2 *Incident infection*

An incident SARS-CoV-2 infection will be defined as the first instance of a positive PCR result that follows at least one negative PCR result. Therefore, for participants who are baseline SARS-CoV-2 positive (i.e. seropositive at first blood collection or PCR positive on first swab), an incident infection occurs only 90 days after the first swab and once there is at least one negative PCR followed by a positive PCR.

3.2.3 *Seroconversion*

A seroconversion event will be defined as the first instance of a positive serology result that follows at least one negative serology result.

3.2.4 *Censoring approaches*

The following analyses will use the following censoring approaches (as specified in analytical approach). For the primary endpoint, “test” refers to a PCR test of a nasal swab. For the secondary endpoint of seroconversion, “test” refers to serology of a blood sample.

- ITT censoring: In the SoC arm, follow-up time is censored at the last negative test prior to end of study vaccination or the last negative test if the participant is not vaccinated on study (both are ignored if the first positive test occurs after the last negative test). In the Immediate Vaccination arm and the Vaccine Declined group, follow-up will be censored at the last negative test (ignored if the first positive test occurs after the last negative test). The timing of any test is considered to be the day on which the assay was collected, where day is defined from 3AM to 3AM of local time of the site.

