7.1 Descriptive analysis

Tables

The following table will be used to describe SARS-CoV-2 incidence by group and vaccine receipt. It will be produced first including only baseline SARS-CoV-2 negative participants, and then again including all FAS-P participants. Each participant's incident exposure period will start from either the first nasal swab (if the first swab result was negative) or 90 days after the first swab (if first swab positive). The participant's exposure will be broken down to unvaccinated, one-dose and two-dose exposure periods. The unvaccinated exposure period will include days and events up to (and including) the date of the first study vaccination or censoring, whichever occurs first. The one-dose exposure period will include days and events starting the day after the first vaccine and ending on the date of the second vaccine or censoring, whichever occurs first. The two-dose exposure period will include days starting the day after the second vaccine. The 95% confidence interval for the incidence rate will be calculated using the exact method.

Group	Exposure: number of study vaccine doses	Censoring	Number of incident infections	Person- years	Incidence rate (95% CI)
Immediate arm	Unvaccinated	Outside vaccination		See note 1	
	Unvaccinated	ITT		See note 1	
	Single dose	Outside vaccination		See note 2	
	Single dose	ITT		See note 2	
	Two doses	Outside vaccination		See note 3	
	Two doses	ITT		See note 3	
SoC arm	Unvaccinated	Outside vaccination		See note 4	
	Unvaccinated	ITT		See note 4	
Vaccine Declined arm	Unvaccinated	Outside vaccination		See note 4	
	Unvaccinated	ITT		See note 4	

Note 1: Total number of person-years from the incident follow-up start to the first of study vaccination, infection or censoring.

Note 2: Total number of person-years from the last of incident follow-up start and first dose to the first of second dose, infection or censoring.

Note 3: Total number of person-years from the last of incident follow-up start and second dose to the first of infection or censoring.

Note 4: Total number of person-years from the incident follow-up start to the first of infection or censoring.

Incident follow-up start = either the first nasal swab (if the first swab result was negative) or 90 days after the first swab (if first swab positive)

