7.2.1 Supportive analyses

- **ITT analysis:** We will repeat the primary analysis using ITT censoring.
- **All FAS analysis:** includes those baseline SARS-CoV-2 negative and baseline SARS-CoV-2 positive in the analysis.

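### The 90-day wait for an incident infection covers seropositive participants, but the 90-day delay in starting follow-up does not, so FAS-P rates include time that cannot yield an event

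*SAP*

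**What the plan says.** **Event rule (SAP 3.2.2).** An incident infection is "defined as the first instance of a positive PCR result that follows at least one negative PCR result". A second sentence, offered as a consequence of the first, adds a wait for anyone baseline positive: "i.e. seropositive at first blood collection or PCR positive on first swab), an incident infection occurs only 90 days after the first swab".

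**Start of follow-up (SAP 3.2.1 and 7.1).** Study time begins at the first "nasal swab (if the first swab result was negative) or 90 days after the first swab (if first swab positive"). The incidence table uses the same start: "Each participant's incident exposure period will start from either the first nasal swab (if the first swab result was negative) or 90 days" later if it was positive. The table's note on incident follow-up start repeats this. Serostatus appears in none of these places.

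**Denominator (SAP 7.1, note 4).** "Total number of person-years from the incident follow-up start to the first of infection or censoring".

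**Where baseline-positive participants enter.** The incidence table is produced for baseline-negative participants "and then again including all FAS-P participants". The All FAS supportive analysis in SAP 7.2.1 "includes those baseline SARS-CoV-2 negative and baseline SARS-CoV-2 positive in the analysis". The primary analysis in SAP 7.2 is limited to baseline-negative participants enrolled as randomized.

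**The concern.** A rate is valid only if the time counted as at risk is time in which an event could be recorded. The SAP achieves this for participants whose first swab is PCR positive, because both their events and their follow-up start at day 90. It does not for those who are seropositive with a negative first swab. They accrue person-time from that swab, yet under the second sentence of 3.2.2 a positive PCR on, say, day 40 is not an incident infection. The time before day 90 enters the denominator with no possible numerator.

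The first sentence of 3.2.2 would count that day-40 positive, since it follows a negative swab. Two programmers could therefore derive different event counts from the same data.

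At stake are the FAS-P incidence rates and, if the same start applies there, the All FAS Cox analysis. The latter is the SAP's VE analysis for the infection part of secondary objective 5, which disregards baseline serostatus.

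**Working it through.** The documents give no figure for this effect, so there is none to reproduce. Observed seropositivity and follow-up are not reported, so the sizes below are scenarios.

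**Inputs**
- Blocked period: 90 days from the first swab (SAP 3.2.2).
- Swabbing period: D1 to D113, about 112 days (Protocol Appendix F, note 4). SAP 3.2.7 caps it at 111 days after enrollment.
- Baseline seropositivity p: 10% (Protocol Table 6-2). Other values are assumptions. All seropositive participants are taken to have a negative first swab.
- Incidence without vaccination: 4% over 16 weeks at a constant rate (Protocol Table 6-2).
- Doses at days 0 and 28, counted from the first swab.
- r: hazard in seropositive relative to seronegative participants. r = 1 unless stated (an assumption).

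**Step 1. Blocked share of one participant's time.** 90/112 = 80%. It is 100% for anyone followed 90 days or less.

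**Step 2. Blocked share of all FAS-P time** = p × 90/112: 4.0%, 8.0%, 16.1% and 24.1% for p = 5%, 10%, 20% and 30%.

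**Step 3. Recorded rate relative to the rate with matching windows, p = 10%.** Index = (1 − p) + p × r × (days after day 90 in the row / days in the row).

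| Row | Days | Days after day 90 | Index | Understated by |
|---|---|---|---|---|
| SoC, unvaccinated | 0–112 | 22 | 0.90 + 0.10 × 22/112 = 0.920 | 8.0% |
| Single dose | 0–28 | 0 | 0.90 + 0 = 0.900 | 10.0% |
| Two doses | 28–112 | 22 | 0.90 + 0.10 × 22/84 = 0.926 | 7.4% |

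The design incidence is −ln(0.96)/(112/365.25) = 0.133 per person-year. The unvaccinated rate would be recorded as 0.133 × 0.920 = 0.122.

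**Step 4. Effect on VE when the true effect is nil** (crude rate ratios, not calendar-time Cox estimates)
- One dose, p = 10% in both arms: 1 − 0.900/0.9196 = +2.1%.
- Two doses, p = 10% in both arms: 1 − 0.9262/0.9196 = −0.7%.
- Two doses, SoC follow-up ended by day 90 through outside vaccination: 1 − 0.9262/0.900 = −2.9%.
- Two doses, Immediate 10% and SoC 15%: the SoC index is 0.85 + 0.15 × 22/112 = 0.8795, giving 1 − 0.9262/0.8795 = −5.3%.
- Two doses, Immediate 15% and SoC 10%: the two-dose index is 0.85 + 0.15 × 22/84 = 0.8893, giving 1 − 0.8893/0.9196 = +3.3%.

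**Step 5. Does entry at day 90 recover the all-comer rate?** Take p = 10% over 112 days. The true index is 0.90 + 0.10r. As written it is 0.90 + 0.10r × 22/112. With entry at day 90 it is (0.90 × 112 + 0.10r × 22)/(0.90 × 112 + 0.10 × 22) = (100.8 + 2.2r)/103.

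| r | True | As written (error) | Entry at day 90 (error) |
|---|---|---|---|
| 1 | 1.000 | 0.920 (−8.0%) | 1.000 (0%) |
| 0.5 | 0.950 | 0.910 (−4.2%) | 0.989 (+4.1%) |
| 0.2 | 0.920 | 0.904 (−1.7%) | 0.983 (+6.8%) |

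Entry at day 90 makes the windows match but gives seropositive participants less weight.

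**The case against.** **The mention of seropositivity in 3.2.2 may be a drafting slip.** Its second sentence does not follow from the first for someone whose first swab is negative. If the wait was meant only for PCR-positive starters, no time is blocked. But the clause defining baseline positive names seropositivity explicitly, and on that reading 3.2.2 itself would need correcting. The reading changes which sentence to edit, not whether an edit is needed.

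**The reach is limited.** This stands, and several stronger inferences fail.
- A reader might infer that the primary VE estimate is biased. It is not, because SAP 7.2 excludes baseline-positive participants.
- A reader might infer that the monthly and Kaplan-Meier plots are wrong. SAP 7.1 states the FAS-P repeat for the table only; the plots are affected only if they include seropositive participants.
- A reader might carry the 8% to 10% understatement over to VE. Most of it cancels between randomized arms with similar seropositivity and follow-up.
- A reader might expect the Vaccine Declined group to distort the All FAS VE, because Protocol 7.4, unlike 7.2, does not exclude known prior infection. SAP 3.1 limits VE estimation in FAS-P to participants enrolled as randomized, so this concerns only that group's descriptive rate.
- The effect on the All FAS Cox model is inferred, because SAP 7.2 gives no entry rule for the risk set.

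**Delayed entry is not a neutral repair.** This also stands. If prior infection protects, entry at day 90 overstates the all-comer rate (step 5).

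**Conclusion.** The mismatch is in the text and makes the FAS-P incidence table wrong as written, because no provision removes the blocked time. At 10% seropositivity, full 112-day follow-up and equal hazards, rates are about 8%, 10% and 7% too low for unvaccinated, single-dose and two-dose time. With a lower hazard after prior infection, the shortfall against the true all-comer rate is smaller: 4.2% at r = 0.5 and 1.7% at r = 0.2 for unvaccinated time. The Vaccine Declined rate may be diluted more, but the documents do not show by how much.

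For the All FAS Cox analysis the conclusion is conditional on the 7.1 start carrying over. The crude VE shift is then about +2 points for one dose and −0.7 points for two with balanced seropositivity, and roughly −5 to +3 points for two doses with a 5-point imbalance.

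This is a should-fix for secondary and supportive outputs. The SAP already describes the study as underpowered for its primary objectives, and the primary analysis does not depend on this rule.

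**What to change.** Use one criterion for the event rule and the start of follow-up in SAP 3.2.1, 3.2.2, 7.1 and the note on incident follow-up start, and state the same entry rule for the All FAS Cox model. Either option works:

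- **(a)** Start follow-up at day 90 for every baseline-positive participant, whether by serology or PCR. Say that this down-weights seropositive time and drops those followed for less than 90 days.
- **(b)** For seropositive participants with a negative first swab, count events from that swab and apply the 90-day wait only to PCR-positive starters. This keeps their time, agrees with the first sentence of 3.2.2 and fits secondary objective 5 better.

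State also whether the 7.1 plots include seropositive participants. SAP 3.2.5 needs no change, because its models use baseline-negative participants only. The cost is a short text edit and a re-run of the FAS-P table and the All FAS model, with no new data.

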Baseline variables to be assessed: Age, sex, race/ethnicity, place of residence, attributes from the Baseline SARS-CoV-2 Infection Risk Assessment CRF

Due to small numbers in some groups, race/ethnicity will be dichotomized as under-represented minority, defined as Black or African American, American Indian or Alaska Native or Native Hawaiian or Other Pacific Islander race or Hispanic or Latino ethnicity. Place of residence will be categorized into four groups: 1. "Apartment building or condo", 2. Dorm/campus housing/frat/sorority (combines "Dormitory or campus housing" and "Fraternity or sorority house"), 3. "Stand-alone house (non-fraternity or sorority)" and 4. "Other" (combines all other categories).

Selection of variables to study will be informed by an assessment of data completeness. Variables missing for more than 10% of records to be included in the analysis will be excluded from consideration. Single imputation will be used to fill in missing records for the variables that are selected for study.

3.2.6 SARS-CoV-2 exposure

Given the open-label nature of the study, it is possible that individuals in the Immediate Vaccination, SoC, and Vaccine Declined groups have different exposure to SARS-CoV-2. While the randomized groups are ensured to balance with respect to baseline factors, individuals in the Vaccine Declined Group are likely to differ from those in the randomized groups based on both baseline and time-varying factors related to exposure. Imbalanced exposure between groups may lead to bias in analyses that compare endpoint distributions between groups. A series of analyses will explore predictors of SARS-CoV-2 exposure based on baseline SARS-CoV-2 negative participants in the SoC group. Separate but identical analyses will explore predictors of exposure in the Vaccine Declined group.

The outcome of interest will be time to incident infection. Calendar time will be the time scale and participants will be censored using 'outside testing censoring'. Baseline and time-varying variables listed above in Section 3.2.5 will be screened univariately for their associations with SARS-CoV-2 infection based on Cox proportional hazards models that stratify on study site. Variables with p-values less than 0.10 will be retained. Retained baseline variables will be screened further to remove highly correlated variables; for pairs with absolute value of Spearman correlation > 0.90 , a randomly chosen member of the pair will be retained. Cox regression with lasso penalty, stratified on study site and implemented with glmnet and with the retained variables from the previous step, will be used to derive a 'risk score' that is used for

adjustment in multiple analyses described below. The linear predictor of the penalized Cox model will be used as the risk score. This risk score will be included as a covariate in efficacy analyses described in Section 7.

3.2.7 *Noncompliance with swabbing*

Noncompliance with daily nasal swabbing may result in missed endpoints and incompletely observed viral load trajectories.

Alluvial plots will be used to explore noncompliance over study and calendar time, by enrollment group and study site and other baseline covariates. Descriptive tables will summarize noncompliance over study time by enrollment group. Compliance will be defined in two ways, with swabs expected starting from either 1. enrollment date or 2. first swab date (or enrollment date if participant had no swabs). Days with a swab will be expected until minimum of the day before the date CRF-confirmed study completion, 111 days after enrollment and the last expected swabbing date (Dec. 31, 2021). Additionally, swabs will not be expected after outside vaccination

or termination. Time (weeks) after these two events (outside vaccination and termination) will be displayed separately in the plots. Compliance metric for participant weeks with at least one expected swab day will be the % (of expected) days with a swab, categorized as 0%, 1-29%, 30-58% and 59-100% (these categories will be labelled as 0, 1-2, 3-4 and 5-7, respectively, corresponding to a week with 7 expected swab days).

A GEE model will be used to explore predictors of time-varying non-compliance. Baseline and time-varying covariates listed in 3.2.5 will be considered for inclusion in the model. Participants will be censored at the earliest of outside vaccination or study termination.

If predictors of non-compliance, other than enrollment group, study time, calendar time, and covariates associated with outside vaccination (Section 3.2.5) or exposure risk (Section 3.2.6) are identified, these will be accounted for in efficacy analyses described in Section 7 through covariate adjustment or IPCW.

3.2.8 *Blood sample exclusions*

Prior to deriving the baseline serostatus and the seroconversion event, the following blood sample data will be excluded to account for replacements or problematic samples:

- Original insufficient in-clinic samples when replacement samples were collected for the same visit (see Section 8 of the Phlebotomy Specimen Collection Study Specific Procedures)
- Self-collected (TASSO) samples resulted as “Test Not Performed” by the lab (due to various reasons, e.g. insufficient/incorrect/damaged/expired/unused sample, processing error)
- In-clinic samples with more than 90 days between blood draw and lab processing
- TASSO samples with more than 7 days between blood draw and lab receipt

3.2.9 *Nasal swab record exclusions*

If duplicate records exist for the same nasal swab, only one record will be retained, and the other records will be excluded from the analysis. The nasal swab data are recorded on two occasions. First, the participants are instructed to scan the swab bar code before application, recording the bar code as an “order number” with the date and time of the scan. Second, the

swab results are recorded when the swab is resulted by the lab (attaching the qualitative result to the order number, date and time). If a given swab order is recorded multiple times (i.e., records with different date-times), the participant likely scanned the same swab multiple times. If that occurs, only the resulted record will be retained (if a result exists; note: multiple results cannot occur) or only the earliest un-resulted record (if no result) will be retained.

Nasal swab results other than “Detected” and “Not Detected” (i.e., “Inconclusive”, “Indeterminate”, “Cancelled. Specimen Issue”, “Invalid Specimen”) will be excluded. Notably, they will be excluded from the first swab result determination which will be allowed to be only positive (“Detected”) or negative (“Not Detected”).

4. GENERAL ANALYSIS METHODS

By-enrollment-group baseline characteristics will be summarized as counts and percentages for categorical variables and median (IQR) for continuous variables. No p-values will be produced for the comparison of the baseline characteristics.

5. TRIAL PARTICIPANT DISPOSITION

5.1 Disposition of Participants

The disposition of trial participants by group will be presented in a CONSORT diagram and table. The disposition, data source and group used to define each variable are described in the table below. The statistic to describe each measure will be the number and the percentage of participants. The table will display also dispositions and the diagram will show selected dispositions.

Disposition(s)	Definition/Data Source	Group(s)	CONSORT diagram
Screened	Any record in the source Sources: Screening Outcome CRF, Participant Type CRF	1. All screened, 2. RCT ¹ screened, 3. Vaccine Declined screened	No (1), Yes (2&3)
Not randomized	Not in Rave randomization or without a randomization arm Source: Rave randomization	RCT screened	Yes
Not randomized, reason	With a given screening status (reason) Sources: Screening Outcome CRF	RCT not randomized	Yes
Not randomized, Ineligible, reason	With a given reason for Ineligibility Sources: Screening Outcome CRF	RCT not randomized and Ineligible	No
Not randomized, Eligible/Not enrolled,	With a given reason for Not Enrolled Sources: Screening Outcome CRF	RCT not randomized	No

Disposition(s)	Definition/Data Source	Group(s)	CONSORT diagram
reason		and Eligible/Not enrolled,	
Randomized	With a randomization arm Source: Rave randomization	RCT ¹ screened	Yes
Randomized, by assignment (Immediate and SoC)	With a given randomization assignment Source: Rave randomization	RCT ¹ screened	Yes
Randomized, Enrolled in the observational arm	Vaccine Declined participant type and enrolled Sources: Participant Type CRF, Screening Outcome CRF	1. Immediate randomized ¹ , 2. SoC randomized ¹	Yes
Not enrolled	Not enrolled screening status Sources: Screening Outcome CRF	1. Immediate randomized, 2. SoC randomized, 3. Vaccine Declined	Yes
Not enrolled, reason	With a given not enrolled screening status (reason) Sources: Screening Outcome CRF	1. Immediate randomized, 2. SoC randomized, 3. Vaccine Declined	Yes
Not enrolled, Ineligible reason	With a given not ineligibility reason Sources: Screening Outcome CRF	1. Immediate randomized, 2. SoC randomized, 3. Vaccine Declined	No
Not enrolled, Eligible/Not enrolled reason	With a given not eligible/not enrolled reason Sources: Screening Outcome CRF	1. Immediate randomized, 2. SoC randomized, 3. Vaccine Declined	No
RCT Enrolled, by arm	Not Vaccine Declined participant type and enrolled Sources: Participant Type CRF, Screening Outcome CRF	1. Immediate randomized, 2. SoC randomized	Yes
Vaccine Declined Enrolled	Enrolled Sources: Screening Outcome CRF	Vaccine Declined	Yes

Disposition(s)	Definition/Data Source	Group(s)	CONSORT diagram
Retrospectively determined ineligible, Not between 18-29 years old	Calculated age at enrollment (enr. date-DOB) is not 18-26 (v1-3) or 18-29 (v4) Sources: Screening Outcome CRF, Demographics e-Diary	1. Immediate enrolled, 2. SoC enrolled, 3. Vaccine Declined enrolled	Yes
Retrospectively determined ineligible, Prior COVID vaccine	Outside vaccination date ² <= enrollment date Sources: Screening Outcome CRF, Outside vaccination CRF	1. Immediate enrolled, 2. SoC enrolled, 3. Vaccine Declined enrolled	Yes
Retrospectively determined ineligible	Not between 18-26/18-29 years old OR prior COVID vaccine See the previous two rows	1. Immediate enrolled, 2. SoC enrolled, 3. Vaccine Declined enrolled	Yes
FAS	Between 18-26/19-29 years old AND no prior COVID vaccine See the previous row (this is a complement)	1. Immediate enrolled, 2. SoC enrolled, 3. Vaccine Declined enrolled	Yes
Without PCR, With study PCR	Participant without vs. with study PCR Source: Study PCR lab data	1. Immediate FAS, 2. SoC FAS, 3. Vaccine Declined FAS	Yes
Baseline SARS-CoV-2 seropositive	Baseline seropositive Source: Serostatus lab data	1. Immediate FAS with study PCR, 2. SoC FAS with study PCR, 3. Vaccine Declined FAS with study PCR	Yes
No qualifying serostatus at baseline	Baseline serostatus unknown among qualifying ³ samples Source: Serostatus lab data	1. Immediate FAS with study PCR, 2. SoC FAS with study PCR,	Yes

Disposition(s)	Definition/Data Source	Group(s)	CONSORT diagram
		3. Vaccine Declined FAS with study PCR	
Baseline SARS-CoV-2 seronegative and PCR positive	Baseline seronegative AND baseline PCR positive Sources: Study PCR and serostatus lab data	1. Immediate FAS with study PCR, 2. SoC FAS with study PCR, 3. Vaccine Declined FAS with study PCR	Yes
Baseline PCR and seronegative	Baseline PCR negative AND baseline seronegative Sources: Study PCR and serostatus lab data	1. Immediate FAS with study PCR, 2. SoC FAS with study PCR, 3. Vaccine Declined FAS with study PCR	Yes
Vaccination status at last study PCR result: “No vaccine” “1 outside vaccine” “2 outside vaccines” “1 study vaccine” “2 study vaccines” “1 study vaccine + 1-2 outside vaccines”	Corresponding number of outside ² &study vaccines on or before the last study PCR result date Sources: Study vaccination CRF, Outside vaccination CRF, Study PCR	1. Immediate FAS with study PCR, 2. SoC FAS with study PCR, 3. Vaccine Declined FAS with study PCR 4. Immediate FAS baseline PCR and seronegative, 5. SoC FAS baseline PCR and seronegative, 6. Vaccine Declined FAS baseline PCR and seronegative	No
End-of-study Vaccination status at last study PCR result: “No vaccine”	Corresponding number of outside ² &study vaccines on or before the termination date Sources: Study vaccination CRF, Outside vaccination CRF, Study Termination CRF	1. Immediate FAS with study PCR, 2. SoC FAS with study PCR,	No (1-3, 6), Yes (4-5)

Disposition(s)	Definition/Data Source	Group(s)	CONSORT diagram
"1 outside vaccine" "2 outside vaccines" "1 study vaccine" "2 study vaccines" "1 study vaccine + 1-2 outside vaccines"		3. Vaccine Declined FAS with study PCR 4. Immediate FAS baseline PCR and seronegative, 5. SoC FAS baseline PCR and seronegative, 6. Vaccine Declined FAS baseline PCR and seronegative	
Vaccine receipt and offer at end of study: "No vaccine before early termination" "1-2 outside vaccines before early termination" "Completed study, not offered vaccine, not vaccinated at end of study" "Completed study, offered vaccine, not vaccinated at end of study" "Completed study with 1-2 outside vaccines by end of study"	Corresponding: - completion (Study Termination CRF = "Scheduled exit visit/end of study") - number of outside ² &study vaccines on or before the termination date - Indication site contacted the participant personally to offer vaccination on site or at an affiliated Walgreens = "Yes" Sources: Outside vaccination CRF, Study Termination CRF, COVID-19 Final Vaccination Status CRF	1. Vaccine Declined FAS with no study PCR, 2. Vaccine Declined FAS with study PCR, 3. Vaccine Declined FAS baseline PCR and seronegative	No (1, 2), Yes (3)
Termination status	Given study termination status Source: Study Termination CRF	1. Immediate FAS with no study PCR, 2. SoC FAS with no study PCR,	No

Disposition(s)	Definition/Data Source	Group(s)	CONSORT diagram
		3. Vaccine Declined FAS with no study PCR, 4. Immediate FAS with study PCR, 5. SoC FAS with study PCR, 6. Vaccine Declined FAS with study PCR	

¹ includes participants screened for RCT, then randomized but enrolled in the Vaccine Declined group. These participants are also counted in the Vaccine Declined group.

² if the date of the first outside vaccine dose was missing and the date for the second one was present, the first date was imputed as the second date minus 28 days.

³ see section 3.2.8

v1-3 = protocol versions 1-3, v4 = protocol version 4

